In order to ensure adequate informed consent, participants will be asked to read the first several lines aloud to determine literacy. If the interviewer determines that the participant is not literate, they will be dismissed from the study but will receive \$20 for attending the screening visit. The participant will be instructed to read several open-ended questions aloud and discuss the answers with the researcher. Only after the participant and the researcher are fully satisfied that the participant understands the purpose of the study, the confidentiality of the data, the procedures, the risks/benefits and his/her rights as a research participant will the consent form be signed electronically via DocuSign and the participant undergo screening procedures. The participant will be emailed a signed electronic copy of the consent document for their records.

Confidentiality and Privacy

Confidentiality will be protected by collecting only information needed to assess study outcomes, minimizing to the fullest extent possible the collection of any information that could directly identify subjects, and maintaining all study information in a secure manner. To help ensure subject privacy and confidentiality, only a unique study identifier will appear on the data collection form. Any collected patient identifying information corresponding to the unique study identifier will be maintained on a linkage file, stored separately from the data. The linkage file will be kept secure, with access limited to designated study personnel. Following data collection subject identifying information will be destroyed (three years after closure of the study; paper documents will be shredded, electronic documents will be securely deleted using software that will delete and overwrite sensitive disk space), consistent with data validation and study design, producing an anonymous analytical data set. Data access will be limited to study staff. Data and records will be

kept locked and secured, with any computer data password protected. No reference to any individual participant will appear in reports, presentations, or publications that may arise from the study.

Data Safety and Monitoring

The principal investigator and co-investigators will be responsible for the overall monitoring of the data and safety of study participants. The principal investigator and co-investigators will be assisted by other members of the study staff.

Potential risks of participation

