10. **Smoking and Oral Contraceptives in Women:** Women who smoke and are over the age of 35 should not take oral contraceptives that contain estrogen without consulting their

physician. Smoking while using oral contraceptives can increase the risk of having a cardiovascular event such as a heart attack or stroke. Additionally, there is a potential risk of thrombosis associated with hormonal therapy (including contraceptives) and smoking.

Avoiding Risks during Pregnancy

Smoking during pregnancy can lead to miscarriage, preterm delivery, stillbirth, birth defects, and other problems. To avoid risks to the participant and fetus, female participants will be tested for pregnancy at the Screening Visit.

Expected benefits of participation

There are no immediate benefits from participating in the study. The information obtained from this study may ultimately help the Food and Drug Administration (FDA) decide how best to regulate tobacco products with the goal of improving public health.

Reporting Unanticipated Problems, Adverse Events or Deviations

Identifying Adverse Events

While participating in the study, adverse events will be assessed at Virtual Visit 6 and carbon monoxide levels from In-Person Lab Visit 3. Adverse events will typically be identified during the administration of the Health Changes Questionnaire. Other adverse events may be identified by spontaneous reports from the participant. Withdrawal symptoms are considered an adverse event if the symptom had a significant impact on the participant's daily life, caused a major disruption of functioning, or took any medication for it.

- Health Changes Questionnaire: If the participant answers "YES" to Questions 1, 2, or 3 the interviewer should assess for adverse events.
 1. Have you had any negative changes in your physical or mental health since your last virtual visit? If yes, briefly describe.
 2. Since your last virtual visit, have you received any form of medical care? If yes, briefly describe.
 3. Have you had any changes in medication since your last visit?

Physiological data that will be reviewed:

1. CO level: The 'Adverse Event Form' will be completed if the average of two (or three) consecutive measurements in the same visit is:
 - o CO is greater than 50 ppm if CO at Screening/Baseline Visit is < 20 ppm.
 - o CO is greater than 60 ppm if CO at Screening/Baseline Visit is 20 – 34 ppm.
 - o CO is greater than 70 ppm if CO at Screening/Baseline Visit is 35 – 49 ppm.

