For the participant's protection, participants will be withdrawn immediately from the study if any of the following occur:

1. Cardiovascular disease (CVD) event: Typically includes MI (heart attack), PTCA (angioplasty/stenting), bypass surgery, stroke, peripheral vascular disease (arterial

blockages in arms or legs leading to procedure or surgery). Less common CVD problems would be new cardiac arrhythmias (e.g., new atrial fibrillation) or new valvular disease (e.g., mitral or aortic regurgitation).

2. DVT/PE (deep vein thrombosis/pulmonary embolism, i.e., blood clots in the venous system).
3. Suicide Attempt: A participant will be withdrawn if they attempt suicide at any time during participation in the study
4. Psychiatric Hospitalization: A participant will be withdrawn if they are hospitalized for psychiatric reasons at any time during participation in the study.
5. Pregnancy: If a participant indicates they are pregnant at Virtual Visit 6 or In-Person Lab Visit 3, they will be withdrawn from the study, and this event will remain open until delivery. At that time the license medical monitor will contact the participant to ask a few questions about the baby's health and will update the open 'Adverse Event Form'.

The following will be monitored and can lead to the participant being withdrawn by the PI or Licensed Medical Monitor:

1. Expired breath CO >80 ppm
2. Any hospitalization or debilitation in which participation in the study could be detrimental to the recovery process. This will be self-reported by the participant and will be reviewed by the site PI and medical monitor to determine whether continued participation in the study is appropriate.
3. If a participant is behaving in an inappropriate or threatening manner, admits to lying about eligibility criteria, including omitting previous medical diagnoses and medications, is participating in other smoking research studies that could affect the primary outcome measures, does not follow study instructions, etc., then the PI can withdraw them from the study at the PI's discretion.
4. If a participant fails to attend her/his Virtual Visit 1 within the 21-day allowable visit window, they will not be eligible to reschedule the visit or continue participation in the study.

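### The pregnancy withdrawal rule names only visits after the seven-day product use, and no pregnancy question is listed at In-Person Lab Visit 2, where take-home products are released (minor safety correction)

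*Combined protocol and SAP*

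**What the plan says.** The immediate-withdrawal list is at the end of the section on reporting unanticipated problems, adverse events or deviations. It opens by saying that "participants will be withdrawn immediately from the study if any of the following occur". Item 5, on pregnancy, then says: "If a participant indicates they are pregnant at Virtual Visit 6 or In-Person Lab Visit 3, they will be withdrawn from the study". The event stays open until delivery, when the medical monitor asks about the baby's health. Item 4 is worded differently: "A participant will be withdrawn if they are hospitalized for psychiatric reasons at any time during participation in the study". Item 3, on suicide attempt, has the same any-time scope. Items 1 and 2 (cardiovascular events and venous clots) carry no time wording.

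Pregnancy is also covered in these places:

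- The Telephone Screening Survey asks about it.
- Exclusion criterion 5 bars pregnancy, intended pregnancy and unwillingness to use adequate protection. The text below the criteria gives possible harm to fetuses and infants as the reason.
- In-Person Lab Visit 1 includes a urine test. The section on avoiding risks during pregnancy mentions no other: "female participants will be tested for pregnancy at the Screening Visit".
- Identifying Adverse Events sets the scheduled assessment: "While participating in the study, adverse events will be assessed at Virtual Visit 6 and carbon monoxide levels from In-Person Lab Visit 3".

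In-Person Lab Visit 2 lists a COVID screener, protective equipment, a temperature check, a CO reading, hand-over of the purchased products and a urine cup. Virtual Visits 2-5 list the tobacco-use interview, two scales and the Experimental Tobacco Marketplace (ETM) task. Neither list contains a pregnancy question.

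**The concern.** The list exists to protect participants, and for pregnancy the exposure the study controls is the week of supplied product. The sentence in item 5 that triggers action names only visits after that week. Taken literally, it cannot operate before products leave the building. A pregnancy reported earlier also has no clearly written follow-up to delivery, because that follow-up belongs to the same event.

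At stake is consistency with the plan's own reason for excluding pregnancy. Someone who became pregnant after the Lab Visit 1 test could be handed products, possibly including cigarettes, and told to use only those for seven days, with no listed step at which anyone asks. This is a participant-safety point. It does not bear on the estimates.

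**Working it through.** The plan gives no figure on this point. The check is a comparison of texts, a visit timeline and a rough count.

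**Wording within the withdrawal list**

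- Lead-in: any occurrence, no time limit.
- Items 1 and 2: no time wording.
- Items 3 and 4: explicitly any time during participation.
- Item 5: two named visits only, the same two that Identifying Adverse Events names for assessment.

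Item 5 can therefore be read as limited to two late visits, or as saying where pregnancy was expected to surface. The text does not settle which.

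**Timeline, with Lab Visit 1 (the test) as day 0**

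Inputs: Virtual Visit 2 is 1 to 21 days after Lab Visit 1. Virtual Visits 2-5 are ideally on consecutive days (3 days in all), with a 7-day spacing limit. Lab Visit 2 is 0 to 2 days after Virtual Visit 5. Virtual Visit 6 is 7 days after Lab Visit 2. Lab Visit 3 is 0 to 2 days after Virtual Visit 6.

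- Test to hand-out, shortest: 1 + 3 + 0 = 4 days.
- Longest with consecutive virtual visits: 21 + 3 + 2 = 26 days.
- Longest if each of the three gaps may be 7 days: 21 + 3×7 + 2 = 44 days.
- Longest if the 7-day limit covers the whole span of Virtual Visits 2-5: 21 + 7 + 2 = 30 days.
- Hand-out to the visits in item 5: 7 days (Virtual Visit 6) and 7 + 0 to 7 + 2, so 7 to 9 days (Lab Visit 3).

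One visit releases take-home products, and item 5 does not name it. Lab Visit 1 offers only supervised sampling, at the same visit as the test. Virtual Visits 2-5 supply no product. The gap is therefore one contact, Lab Visit 2.

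**Rough count of pregnancies between test and hand-out**

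The documents give neither the sex mix nor an upper age limit, so these inputs are assumptions: 20 to 50 of the up to 100 recruited are of child-bearing potential, and 0.2% to 1% become pregnant per month of 30.44 days.

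Expected number = people × monthly rate × days / 30.44.

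- Low: 20 × 0.002 × 4 / 30.44 = 0.005.
- High rate, 26 days: 50 × 0.01 × 26 / 30.44 = 0.43.
- High rate, 30 days: 50 × 0.01 × 30 / 30.44 = 0.49.
- High rate, 44 days: 50 × 0.01 × 44 / 30.44 = 0.72.

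These are pregnancies arising. The number a question would catch is smaller, since many would not yet be recognised; the documents allow no estimate of it.

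**Effect on the data**

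The primary outcome comes from the four ETM sessions at Virtual Visits 2-5. A participant identified at Lab Visit 2 has completed all 4, so 0 of 4 are lost.

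**The case against.** The strongest reply is that the lead-in already covers pregnancy whenever it occurs, and that item 5 merely repeats the two adverse-event visits. That reading is reasonable and may be how staff apply the list. It does not remove the contrast with items 3 and 4, or supply a question before hand-out.

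Second, absence from a visit list is weak evidence. The protocol says "Adverse events will typically be identified during the administration of the Health Changes Questionnaire", yet that questionnaire is missing from the Virtual Visit 6 list, so something may be asked at Lab Visit 2 without being listed. This stands. The questionnaire would not close the gap, though: it is tied to Virtual Visit 6 and has no explicit pregnancy question.

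Third, there is partial cover. Participants must be willing to use protection. On reporting, "Other adverse events may be identified by spontaneous reports from the participant". On oversight, "The principal investigator and co-investigators will be responsible for the overall monitoring of the data and safety of study participants". The principal investigator also has discretion to withdraw. All of this helps, but none of it is a scheduled check before release.

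Fourth, participants already smoke at least 5 cigarettes a day, and field products may be e-liquid, gum or nothing. Withholding them may simply mean a return to usual smoking. This stands: the study would stop supplying product, but a net fall in exposure is not shown.

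Fifth, full withdrawal at any time would sacrifice primary data at visits that supply no product. A participant who reported pregnancy before the task at Virtual Visit 2, 3, 4 or 5 would lose 4, 3, 2 or 1 of her 4 sessions. This also stands, and it is why the remedy below is directed at product release and keeps completed sessions.

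**Conclusion.** The point holds as a minor participant-safety correction. Item 5 names only visits 7 to 9 days after hand-out. The one visit that releases take-home products lists no pregnancy question, and the only test is then 4 to 44 days old, or at most 30 on the narrower reading of the spacing rule. Fewer than one affected participant is expected (0.005 to 0.72), and that range rests wholly on the assumed numbers and rates. There is no effect on power or the primary analysis.

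A reader might go further and infer that the plan directs staff to give products to someone known to be pregnant, or that pregnancy before Virtual Visit 6 is outside the rule. The documents support neither: the lead-in is open-ended, pregnancy is an exclusion with a stated fetal-harm reason, and nothing instructs release in that case. Nor do they support a claim that measurable fetal exposure would be avoided, given continued daily smoking and at most about a week of supplied product.

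**What to change.** 1. At In-Person Lab Visit 2, repeat the telephone-screen pregnancy question before products are handed over.
2. Reword item 5 so that a pregnancy reported at any time during participation means that no study products are released, or that any already released are stopped and returned, and that the event is followed to delivery. State that ETM sessions already completed are kept.

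No repeat urine test is needed. The cost is one question at a visit that already takes place and a change to one list item. A question will miss unrecognised pregnancy. The downside is that a participant identified at Lab Visit 2 contributes no field-week data; with fewer than one expected, against a recruitment allowance of 100 − 80 = 20, that loss is acceptable.
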